8.3. Exploratory Efficacy Analyses

A Poisson regression model will be fit to estimate the rate of positive BV diagnoses through Visit 4 (Week 12) in each of the treatment arms and to compare the rate in the LACTIN-V arm to that in the placebo arm. The outcome of the model will be the number of positive BV diagnosis after enrollment and through Visit 4 and the model will include a covariate for treatment group and an offset term of log(follow-up time). The offset is included in the model as not all subjects will be followed up through Visit 4 (e.g. subjects who are lost to follow-up prior to Visit 4) and so subjects will have variable follow-up times. The follow-up time variable in the model will be the elapsed time (in days) from randomization to the earliest of the following: Visit 4 date, date of censoring from the particular analysis population, or the termination date. [Table 67](#) will present the treatment group-specific rates of BV (and 95% confidence interval) along with the rate ratio between treatment groups (and 95% confidence interval).

A repeated measures logistic regression model will be fit to estimate the odds of a positive BV diagnosis through Visit 4 (Week 12) in each of the treatment arms and to compare the odds of a BV diagnosis in the LACTIN-V arm to that in the placebo arm. The marginal model to be used will have covariates for treatment group, time, and a treatment by time interaction, i.e. the model is of the form:

$$g(E[Y_{ij}]) = \beta_0 + \delta_i\beta_1 + t_{ij}\beta_2 + \delta_it_{ij}\beta_3 + \epsilon_{ij}$$

where $g(\cdot)$ is the logit function, Y_{ij} is the BV diagnosis status of subject i at visit j , δ_i is the indicator function for the treatment group of subject i ($\delta_i = 1$ for LACTIN-V and $\delta_i = 0$ for Placebo), and t_{ij} is time (in study days) at which visit j occurred for subject i . The visits included in the model will be Visit 2 (Week 4) through Visit 4 (Week 12) and each subject will be included from the time of the first administration of study product to the earliest of the following: Visit 4 date, date of exclusion from the particular analysis population, or the termination date. Generalized Estimating Equations will be used to fit the model and estimate its parameters. The following working correlation structures will be explored for the assumed covariance among responses within a subject: independent, exchangeable, unstructured, and first-order autoregressive. Model estimates will be compared informally to assess robustness of the estimates with respect to choice of correlation structure. QIC will be also be used to assess model fit with regard to the correlation structure. The model with the lowest QIC will be reported. If inferential differences between the models, this will be noted in the CSR. [Table 68](#) will present the treatment group-specific odds of BV (and 95% confidence interval) along with the odds ratio between treatment groups (and 95% confidence interval).

Select outcome measures will be further broken down by race as an exploratory analysis. Race will be categorized as Black/African American, White, and Other. The following summaries will be generated:

- BV recurrence by Visit 4 (Week 12) by analysis population, treatment group, and race ([Table 69](#)). Analyses will follow those for [Table 11](#).
- BV recurrence by Visit 7 (Week 24) by analysis population, treatment group, and race ([Table 70](#)). Analysis will follow those for [Table 12](#).
- *L. crispatus* colonization through Visit 4 (Week 12) by analysis population, treatment group, and race ([Table 71](#)). Analysis will follow those for [Table 21](#).

-
- *L. crispatus* colonization at Visit 7 (Week 24) by analysis population, treatment group, and race (Table 72). Analyses will follow those for Table 22.
 - *L. crispatus* CTV-05 concentration by study day, treatment group, and race (Table 73, Table 74, Table 75, and Table 76). Analysis will follow those for Tables 27 – 30.

Additional summaries of the *L. crispatus* colonization and CTV-05 concentration will be generated as exploratory analyses. Figures of CTV-05 concentration by *L. crispatus* concentration will be generated for each treatment group and study day (Figure 29, Figure 30, Figure 31, and Figure 32). CTV-05 concentration and *L. crispatus* colonization will be further broken down by Amsel criteria and Nugent score. Summaries *L. crispatus* colonization (Yes/No) will be presented by Amsel criteria status (Positive/Negative) (Table 77, Table 78, Table 79, and Table 80) and Nugent score category (Normal/Indeterminate/BV) (Table 81, Table 82, Table 83, and Table 84), following the analyses for Tables 23 - 26. See Section 3.3.1 for Amsel criteria and Nugent score category definitions. Similar summaries will be generated for *L. crispatus* CTV-05 concentration (Table 85, Table 86, Table 87, Table 88, Table 89, Table 90, and Table 91). Boxplots of *L. crispatus* CTV-05 concentration by Amsel Criteria/Nugent Score will be generated for each treatment group and study day (Figure 33, Figure 34, Figure 35, Figure 36, Figure 37, Figure 38, Figure 39, and Figure 40). Listing 6 will provide a listing individual efficacy data.

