Women who develop *symptomatic* BV confirmed by wet mount Amsel criteria ≥ 3 (with or without confirmatory Gram stain) at least 4 weeks after the last MetroGel treatment will be retreated with MetroGel. This practice follows CDC treatment guidelines and FDA recommendations. The 5-day course of MetroGel will begin as soon as possible. Women will skip their regularly scheduled dose of study product until 24 hours after their last dose of MetroGel when study product dosing will continue twice weekly. Women diagnosed with *asymptomatic* BV during the follow-up visit will not be retreated with MetroGel.

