7.4 Follow-up Study Visit 3, Week 8, Day 56 (Allowable Days 49-63)

The same procedures and assessments performed at Study Visit 2, Week 4, Day 28 will also be done at this visit.

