3.3.2. Recurrent BV

By standard definition, a treatment of BV is only considered to have failed if Amsel criteria or Nugent score on Gram stain diagnose BV to persist at 22-30 days after the initiation of the antibiotic treatment. As a result, women who continue to have BV during the enrollment visit will not be re-treated with MetroGel at the time of enrollment, as additional time is needed for BV to resolve after antibiotic treatment. Thus, they are not considered treatment failures at this time (approximately 2 days after termination of antibiotic treatment). All BV diagnoses following enrollment are considered incident, as they occur at least 22-30 days after the commencement of MetroGel treatment and consequently are treatment failures or new infections. And so, a positive diagnosis of BV at any visit after the enrollment visit will be considered a recurrence of BV (i.e. there

is no distinction between treatment failure and new infection). A positive diagnosis of BV at the enrollment visit will not be considered a recurrence of BV.

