6.1.1. Pseudo Code

The following SAS® pseudo code will be used to calculate the following:

Chi-Square test at 5% two-sided significance level and odds ratio (and 95% asymptotic CI) from 2x2 table:

```
proc freq;
  Table treatment*analysis_variable / chisq;
  ods output ChiSq=outputdsn1;
  ods output RelativeRisks=outputdsn2;
run;
```

Fisher's Exact test at 5% two-sided significance level:

```
proc freq;
  Table treatment*analysis_variable / exact;
  ods output FishersExact=outputdsn;
run;
```

95% Wilson CI for proportions/percentages:

```
proc freq;
  Table treatment*analysisvariable / binomial(wilson);
  ods output binomialcls=outputdsn;
run;
```

95% Wilson CI for difference in proportions (produces Newcombe CI):

```
proc freq;  
  Table treatment*analysisvariable / riskdiff(cl=Wilson);  
  Exact Riskdiff;  
  ods output pdiffcls=outputdsn;  
run;
```

95% Exact Blaker CI for proportions/percentages:

```
proc freq;  
  Table treatment*analysisvariable / binomial(blaker);  
  ods output binomialcls=outputdsn;  
run;
```

Time to event analysis to estimate number of events, median (and other quartiles) time to event, and Kaplan-Meier curves:

```
ods output CensoredSummary =_censorsum Quartiles =_quartiles;  
proc lifetest plots=survival;  
  time studyday*eventstatus(0);  
  strata treatment;  
run;
```

Poisson regression analysis to estimate event rate in each treatment group and rate ratio between treatment groups (with associated 95% CIs):

```
proc genmod;  
  class treatment;  
  model eventcount = treatment / dist=poisson link=log offset=logfollowuptime;  
  lsmeans treatment / ilink diff cl;  
run;
```

Repeated measures logistic regression analysis using Generalized Estimating Equations to estimate odds of event in each treatment group and odds ratio between treatment groups (with associated 95% CIs):

```
proc genmod;  
  class subjectid treatment other_covariates / param=glm;  
  model outcome=treatment other_covariates / dist=bin;  
  repeated subject=subjectid / type=ind/un/exch/ar(1);  
  lsmeans treatment / ilink exp diff cl;  
run;
```

Smoothing spline regression with different curves for each treatment group (with 95% confidence bands):

```
proc transreg;  
  model identity(outcome) = class(treatment / zero=none) | spline(day / knots=0 to  
  max_day by 1);  
run;
```

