On a scale of 0 to 10, with 0 being “not at all important” to 10 being “extremely important”, I would find the following characteristics important about such a product:	Effective to treat BV	xx.x (xx.xx)	xx.xx	xx.x, xx.x	xx.x (xx.xx)	xx.xx	xx.x, xx.x
	Comfortable	xx.x (xx.xx)	xx.xx	xx.x, xx.x	xx.x (xx.xx)	xx.xx	xx.x, xx.x
	Easy to use	xx.x (xx.xx)	xx.xx	xx.x, xx.x	xx.x (xx.xx)	xx.xx	xx.x, xx.x
	Improved vaginal prescription	xx.x (xx.xx)	xx.xx	xx.x, xx.x	xx.x (xx.xx)	xx.xx	xx.x, xx.x
	Availability without prescription	xx.x (xx.xx)	xx.xx	xx.x, xx.x	xx.x (xx.xx)	xx.xx	xx.x, xx.x
	All-natural ingredients of the product	xx.x (xx.xx)	xx.xx	xx.x, xx.x	xx.x (xx.xx)	xx.xx	xx.x, xx.x
	Partner’s approval of the product	xx.x (xx.xx)	xx.xx	xx.x, xx.x	xx.x (xx.xx)	xx.xx	xx.x, xx.x
	Other	xx.x (xx.xx)	xx.xx	xx.x, xx.x	xx.x (xx.xx)	xx.xx	xx.x, xx.x
Etc.							
Note: N= number of subjects in the Safety Population in the respective treatment group							

Tables with similar format:

Table 66: Continuous/Discrete Responses to Acceptability Questionnaire by Treatment Group – Visit 4 (Week 12)

Table 67: Model-Based Rate of Positive BV Diagnoses by Visit 4 (Week 12) by Analysis Population and Treatment Group

Analysis Population	Treatment Group	Number of Subjects N	Rate of BV Diagnoses n	BV Diagnosis Rate 95% CI	BV Diagnosis Rate Ratio between LACTIN-V Group and Placebo Group	BV Diagnosis Rate Ratio between LACTIN-V Group and Placebo Group 95% CI
ITT	LACTIN-V	x	x.xx	x.xx, x.xx	x.xx	x.xx, x.xx
	Placebo	x	x.xx	x.xx, x.xx	--	--
	All Subjects	x	x.xx	x.xx, x.xx	--	--
mITT	LACTIN-V	x	x.xx	x.xx, x.xx	x.xx	x.xx, x.xx
	Placebo	x	x.xx	x.xx, x.xx	--	--
	All Subjects	x	x.xx	x.xx, x.xx	--	--
CC	LACTIN-V	x	x.xx	x.xx, x.xx	x.xx	x.xx, x.xx
	Placebo	x	x.xx	x.xx, x.xx	--	--
	All Subjects	x	x.xx	x.xx, x.xx	--	--
PP	LACTIN-V	x	x.xx	x.xx, x.xx	x.xx	x.xx, x.xx
	Placebo	x	x.xx	x.xx, x.xx	--	--
	All Subjects	x	x.xx	x.xx, x.xx	--	--

Table 68: Model-Based Odds of Positive BV Diagnoses by Visit 4 (Week 12) by Analysis Population and Treatment Group

Analysis Population	Treatment Group	Number of Subjects N	Odds of BV Diagnoses n	BV Diagnosis Odds 95% CI	BV Diagnosis Odds Ratio between LACTIN-V Group and Placebo Group	BV Diagnosis Odds Ratio between LACTIN-V Group and Placebo Group 95% CI
ITT	LACTIN-V	x	x.xx	x.xx, x.xx	x.xx	x.xx, x.xx
	Placebo	x	x.xx	x.xx, x.xx	--	--
	All Subjects	x	x.xx	x.xx, x.xx	--	--
mITT	LACTIN-V	x	x.xx	x.xx, x.xx	x.xx	x.xx, x.xx
	Placebo	x	x.xx	x.xx, x.xx	--	--

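### The exploratory rate-ratio interval in SAP Table 67 assumes Poisson variance; a sandwich variance, already used for Table 68, would be safer at almost no cost

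*SAP*

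**What the plan says.** SAP 8.3 fits two models to BV diagnoses through Visit 4.

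- **Poisson model (Table 67).** "The outcome of the model will be the number of positive BV diagnosis after enrollment and through Visit 4", with treatment as the only covariate and log follow-up time as offset. The code in SAP 6.1.1 is `class treatment`, then "model eventcount = treatment / dist=poisson link=log offset=logfollowuptime", then LSMEANS with confidence limits. It has no REPEATED statement and no scale option, and SAP 8.3 names no variance estimator. The table reports arm-specific rates and the "BV Diagnosis Rate Ratio between LACTIN-V Group and Placebo Group 95% CI".
- **Logistic model (Table 68).** "Generalized Estimating Equations will be used to fit the model and estimate its parameters", and the code carries "repeated subject=subjectid / type=ind/un/exch/ar(1"). The table reports an odds ratio.

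Three other places bear on the count:

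- SAP 3.3.2: "a positive diagnosis of BV at any visit after the enrollment visit will be considered a recurrence of BV".
- Protocol 7.3, of women whose BV is asymptomatic: "BV during the follow-up visit will not be retreated with MetroGel". Women with symptomatic BV are retreated.
- Protocol 7.4, for Visit 3: "The same procedures and assessments performed at Study Visit 2, Week 4, Day 28 will also be done at this visit".

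Protocol 11.6.1 undertakes in general terms to validate model assumptions. Neither document names a dispersion check or a robust interval for this model.

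**The concern.** An ordinary Poisson fit takes its standard errors from the assumption that variance equals mean. Here each woman's count is a sum of a few yes/no results, and two forces pull against that assumption. A sum of independent yes/no results has variance below its mean, which makes the planned interval slightly too wide. Positive correlation between a woman's visits raises the variance, which makes it too narrow. Untreated asymptomatic BV that is still present at the next visit creates exactly that correlation, and so do lasting differences in risk between women.

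At stake is the interval for the rate ratio that addresses the exploratory objective on repeated episodes. If it is too narrow, it overstates the precision of evidence meant to inform a Phase III trial. Table 68 allows for the correlation, but it estimates an odds ratio and so does not repair the rate-ratio interval.

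**Working it through.** **The plan's own figure.** The documents give no figure for Table 67. The sample size supplies the inputs, so it was reproduced first. With 30% versus 15%, 2:1 allocation, two-sided 5% and 70% power, the pooled proportion is (0.30 + 2×0.15)/3 = 0.20 and

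n(placebo) = [1.96·√(1.5×0.20×0.80) + 0.524·√(0.30×0.70 + 0.15×0.85/2)]² / 0.15² = (0.960 + 0.274)²/0.0225 ≈ 67.7, so 68.

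That is 204 in total, and 204/0.9 gives 227 against the stated 228. With 205 completers the power is 0.704. Taking 90% of 228 (205) split 2:1 gives 68 placebo and 137 LACTIN-V women.

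**Model for the counts.** Visits 2, 3 and 4 are assessed. The per-visit hazard is h = 1 − (1 − P)^(1/3), which is 0.112 for P = 0.30 and 0.053 for P = 0.15. After a positive visit, BV persists to the next visit with probability s; otherwise a new positive occurs with the same hazard h. The documents do not give s. It is an assumption, taken as equal in both arms.

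With d = s(1 − h), the visit probabilities are p₁ = h, p₂ = h + p₁d and p₃ = h + p₂d. With vⱼ = pⱼ(1 − pⱼ):

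- mean m = p₁ + p₂ + p₃
- variance V = v₁ + v₂ + v₃ + 2(v₁d + v₂d + v₁d²)

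Placebo at s = 0.5: d = 0.444 and p = 0.112, 0.162, 0.184, so m = 0.458. The variance is 0.385 + 2(0.044 + 0.060 + 0.020) = 0.633, and V/m = 1.38.

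**Standard errors of the log rate ratio** (0 = placebo, 1 = LACTIN-V):

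- Poisson: √[1/(68m₀) + 1/(137m₁)]
- Sandwich: √[V₀/(68m₀²) + V₁/(137m₁²)]

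At s = 0.5, m₁ = 0.220 and V₁ = 0.341. The two standard errors are 0.256 and 0.310, a ratio of 1.21.

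**Results** (coverage from 60,000 simulated trials per value of s; repeat runs agreed to within 0.3 percentage points):

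| s | Placebo V/m | Sandwich SE / Poisson SE | Coverage of planned 95% CI |
|---|---|---|---|
| 0 | 0.89 | 0.96 | 96.4% |
| 0.1 | 0.99 | 1.01 | 94.9% |
| 0.25 | 1.14 | 1.09 | 93.1% |
| 0.5 | 1.38 | 1.21 | 89.9% |

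The unrealistic bound s = 1 gives 84.6%. Sandwich coverage was 94.9–95.3% throughout.

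**Fitted models.** A Poisson GLM and a Poisson GEE (independence, follow-up of 77–91 days, 1,500 trials) covered 96.2% and 95.1% at s = 0, 95.1% and 95.3% at s = 0.1, 93.1% and 94.9% at s = 0.25, and 90.7% and 96.0% at s = 0.5. Their log rate ratios agreed to within 3×10⁻¹⁰.

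**Sensitivity of the planned interval's coverage:**

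- *Retreatment.* Suppose retreated symptomatic BV always clears and asymptomatic BV persists with probability 0.5. If 25%, 50% or 75% of positives are asymptomatic, the effective s is 0.5 times that share (0.125, 0.25, 0.375) and coverage is about 95%, 93% or 91%.
- *Other recurrence rates.* For s = 0, 0.1, 0.25 and 0.5, 30% in both arms gives 96.6, 95.4, 93.6 and 90.7%; 45% versus 22.5% gives 96.6, 95.6, 93.9 and 91.2%.
- *Varying risk without persistence.* With intra-woman correlation of 0.05, 0.1 or 0.2, coverage is 94.9, 94.2 or 92.2%. A separate beta-binomial simulation at 0.2 gave 92.5%, against 94.9% for the sandwich.
- *Unscheduled visits.* SAP 8.3 does not restrict the count to scheduled visits. If a positive woman has a 10% chance of one extra counted positive in the same interval, coverage is 94.4, 92.8, 90.7 and 87.5% for s = 0, 0.1, 0.25 and 0.5. This case is conditional: SAP 4.5 keeps one assessment per visit window, so only positives falling between windows could add to the count.

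**The case against.** The strongest reply is that the two models are not in conflict. The logistic model has several records per woman and needs a repeated-subject structure; the Poisson model has one count per woman, so its records are independent and the only question is dispersion. That is true, but it restates the issue, because correlation between visits is what makes a woman's count over-dispersed. The sandwich variance handles it with one record per woman.

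Second, neither the size nor the direction of the error is fixed by the documents. By the figures above the planned interval is conservative at s = 0 and about right near s = 0.1, and at scheduled visits coverage near 90% needs s of about 0.5. This stands, and it limits the priority. It also favours a method that does not depend on knowing s.

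Third, protocol 11.6.1 promises validation of assumptions and allows goodness-of-fit checks, and the SAP code is labelled pseudo code. But SAP 6.1.1 says that code will be used, and no check or fallback is specified for this model.

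Fourth, Table 67 has no p-value, and the analysis is exploratory with no multiplicity control. This also stands.

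**Conclusion.** The concern holds, at low priority. As written, the Table 67 intervals are valid only if each woman's count has variance equal to its mean, and nothing in the design secures that. With persistence between visits from 0 to 0.5, coverage of the nominal 95% rate-ratio interval runs from 96.4% down to 89.9%, while the sandwich interval stays close to 95%. These figures rest on three scheduled visits, the plan's recurrence rates and dropout, equal persistence in both arms, and a value of s that the documents do not supply. The missing variance option can be read directly from the SAP; how much it matters depends on s. The rate-ratio estimate, the primary chi-square test and the sample size are unaffected.

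**What to change.** In the Poisson code of SAP 6.1.1, change the CLASS line to `class subjectid treatment;` and add `repeated subject=subjectid / type=ind;`. The CLASS change is needed because the current line lists only treatment. In SAP 8.3, add one sentence stating that the 95% confidence intervals in Table 67 use empirical (sandwich) standard errors. The count, the offset and the table layout stay as they are.

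The cost is two code edits and one sentence, with no new data and no change in point estimates. The downside is usually a somewhat wider interval: over s = 0 to 0.5 the standard error ranges from 4% smaller to 21% larger.

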11.6.4.3 Analysis of Exploratory Efficacy Outcome

The statistical parameterizations of the exploratory objective will include, but are not limited to, the following:

- The number of positive BV diagnoses per 12 weeks of follow-up
- The probability of positive BV diagnoses during the 12 weeks of follow-up

For the first parameterization, a Poisson regression model will be fit to estimate the 12-week incidence of positive BV diagnoses in each of the treatment arms and to compare the incidence in the LACTIN-V arm to that in the placebo arm.

For the second parameterization, a repeated measures logistic regression model will be fit to estimate the probability of positive BV diagnoses in each of the treatment arms and to compare the probability of recurrence in the LACTIN-V arm to that in the placebo arm.

As the exploratory analyses include participants who received additional MetroGel treatment after experiencing symptomatic BV at a particular follow-up visit, a sensitivity analysis will be performed to assess the effect of the additional treatment on the outcome. Details of the sensitivity analysis will be provided in the Statistical Analysis Plan.

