3.1.3. Exploratory Objectives

1. To estimate the efficacy of repeated doses of LACTIN-V (2×10^9 cfu/dose) as compared to placebo in preventing repeated (more than one) episodes of BV recurrence up to 12 weeks following treatment of BV with MetroGel.

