3.2.4. Exploratory Outcome Measures

1. The number of BV recurrences per 12 weeks of follow-up.
2. The probability of BV recurrence during the 12 weeks of follow-up.

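### The exploratory objective concerns repeated episodes of BV, but both planned models analyse positive visits, so one continuing episode can score higher than two separate ones and no output estimates the chance of a second episode.

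*SAP*

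**What the plan says.** Protocol 3.1.3 and SAP 3.1.3 state one exploratory objective: to compare the arms "in preventing repeated (more than one) episodes of BV recurrence up to 12 weeks following treatment of BV with MetroGel". SAP 3.2.4 names the first outcome measure as "The number of BV recurrences per 12 weeks of follow-up". Protocol 11.6.4.3 expresses it as "The number of positive BV diagnoses per 12 weeks of follow-up", and SAP 8.3 makes it concrete for the Poisson model: "The outcome of the model will be the number of positive BV diagnosis after enrollment and through Visit 4". Table 67 is titled as a rate of positive BV diagnoses. The second model in SAP 8.3, a repeated-measures logistic regression, takes BV status at each of Visits 2 to 4 as its outcome.

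Two further rules decide what the count contains. SAP 3.3.2 says that "a positive diagnosis of BV at any visit after the enrollment visit will be considered a recurrence of BV", without requiring a negative visit in between. Protocol 7.3 re-treats symptomatic BV but adds: "Women diagnosed with *asymptomatic* BV during the follow-up visit will not be retreated with MetroGel". Section 7.4 carries this to Visit 3, and 7.5 repeats it for Visit 4.

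Protocol 11.6.4.3 also promises a sensitivity analysis for the effect of re-treatment on the exploratory outcomes and leaves the details to the SAP. The SAP's version, in 8.2 (Tables 19 and 20), covers only the cumulative proportions.

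**The concern.** An episode has a start and an end; a positive visit is a snapshot. Neither document defines an episode, says how to treat consecutive positives, or stops a woman's time at risk while she is still positive. The rule in SAP 4.5 on multiple observations picks one value per visit window and merges nothing across visits. The logistic model estimates the odds of being positive at a visit, which is not the chance of a second episode either.

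A low rate ratio in Table 67 could therefore mean fewer first recurrences, shorter episodes, fewer repeat episodes, or any mixture. A reader who takes it as the answer to the stated objective could credit LACTIN-V with preventing repeat episodes when it had only shortened them. Conversely, if recurrences on LACTIN-V were less often symptomatic, fewer would be re-treated and the count could rise with no more episodes.

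**Working it through.** **1. The plan's own figure.** The plan states no figure for the exploratory outcome. The only design figure is the primary sample size (SAP 5), and it supplies the placebo risk used below. Inputs: 30% against 15%, two-sided 5%, 70% power, 2:1, 10% drop-out.

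n(placebo) = [1.96·√(1.5 × 0.20 × 0.80) + 0.524·√(0.30 × 0.70 + 0.15 × 0.85/2)]² / 0.15² = 67.7, so 68 placebo and 204 in total.

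204/0.9 = 227, against 228 stated. Power at 228 × 0.9 evaluable women is 70.4%. The figure reproduces and is not in dispute.

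**2. What each pattern scores.** There are three scheduled visits (Weeks 4, 8, 12). An episode here needs a negative visit since the last positive.

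| Pattern | Positive visits | Episodes |
|---|---|---|
| +−−, −+−, −−+ | 1 | 1 |
| ++−, −++ | 2 | 1 |
| +−+ | 2 | 2 |
| +++ | 3 | 1 |

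Of the four patterns with two or more positives, only +−+ shows a repeat episode, and +++ outranks it.

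**3. Effect on the rate ratio if persistence is the same or differs.** Illustrative model: constant onset per visit in placebo, 1 − 0.70^(1/3) = 0.112 (30% by Week 12). For LACTIN-V, 1 − 0.85^(1/3) = 0.053. Re-treated symptomatic episodes end before the next visit. Assumptions not in the documents: asymptomatic share 25-75%, and untreated BV still positive at the next visit with probability 50-100%.

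- Positive visits exceed episodes by a factor of 1.11-1.79 in placebo.
- With equal persistence in both arms, the rate ratio is 0.48-0.49 for episodes and 0.48-0.49 for positive visits.
- With equal onset (0.112) but persistence of 30% on LACTIN-V and 90% on placebo, it is 1.01-1.02 for episodes and 0.71-0.87 for positive visits.

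**4. Effect if the asymptomatic share differs.** Assume one episode per recurring woman, with onset equally likely at each of the three visits. Untreated BV stays positive with probability pa (0.6-1.0), and re-treated BV with probability ps (0-0.2). Mean positives per episode for persistence p:

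m(p) = [(1 + p + p²) + (1 + p) + 1]/3

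At pa = 0.8, m = 5.24/3 = 1.747; at ps = 0.2, m = 3.44/3 = 1.147. With 40%, 60% and 80% asymptomatic the score per episode is:

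- 0.4 × 1.747 + 0.6 × 1.147 = 1.387
- 0.6 × 1.747 + 0.4 × 1.147 = 1.507
- 0.8 × 1.747 + 0.2 × 1.147 = 1.627

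With identical episode rates the count ratio is 1.09 (60% against 40%) or 1.17 (80% against 40%). Over the whole range of pa and ps it is 1.06-1.14 and 1.12-1.29. With equal shares and persistence it is 1.00.

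**5. How many repeat episodes to expect.** In the model of step 3, 5.4-16.7% of placebo women have more than one positive visit, but 0.9-2.8% have more than one true episode: 0.7 to 2.1 of the 228/3 = 76 placebo women. That figure includes a woman re-treated at one visit and newly positive at the next. If a negative visit is required, only +−+ counts. With asymptomatic share a, onset p and persistence q, its probability is p²[(1 − a)(1 − p) + a(1 − q)]:

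- a = 0.25, q = 0.5: 0.01257 × (0.666 + 0.125) = 1.0%
- a = 0.75, q = 1: 0.01257 × 0.222 = 0.3%

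That is fewer than one of 76 placebo women.

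**6. Why re-treatment should not define a new episode in the main rule.** If it did, re-treated +++ would score 3 and untreated +++ would score 1. In the model of step 4 with ps = 0.2, symptomatic women would score 1.147 and asymptomatic women 1.00. The ratios would be 1.059/1.088 = 0.97 and 1.029/1.088 = 0.95: smaller than before, but still driven by symptom status, now in the opposite direction.

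**The case against.** The count is declared and labelled for what it is. Protocol 11.6.4.3 names positive diagnoses as one parameterization in an open-ended list, and Table 67 carries the same words. No table claims to show episodes. Within the SAP, the outcome measure agrees with the definition of recurrence in 3.3.2; only the objective's word for episodes does not fit. Pooling treatment failure with new infection is also deliberate. All this stands, and the current count is a legitimate measure of BV burden. But the pooling settles only whether a first positive is a recurrence. It does not make a second and third positive from the same infection into further episodes.

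A reader might infer that the rate ratio is biased. The documents do not support that. The ratios away from 1 in steps 3 and 4 need a difference between arms in persistence or symptoms that nothing in the documents suggests, and with no such difference the ratio hardly moves. A product that shortens BV would properly show less time with BV, which is a different estimand rather than an error.

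Visits are four weeks apart and few repeat episodes are expected, so an episode count will carry limited information. That also stands, and is why the added rows should be descriptive. Diagnoses by visit are in Listing 6, so patterns could be recovered afterwards, but a rule fixed before unblinding is worth more than one chosen later. The analysis is exploratory, and Tables 67 and 68 carry no p-value.

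**Conclusion.** The mismatch is real and follows from the text alone: the objective asks about more than one episode, both models analyse positive visits, +++ scores 3 against 2 for +−+, and nothing planned estimates the chance of a second episode (SAP 10 plans no other analyses). The firmest documentary gap beside it is the promised re-treatment sensitivity analysis, which the SAP does not carry over to the exploratory outcomes.

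The size of any distortion in the rate ratio is conditional. It is negligible if persistence and symptomatic share are alike in both arms. It could be material if they are not, as in the contrast of 0.71-0.87 with 1.01-1.02, which rests wholly on assumed inputs. It would go too far to say that the ratio is wrong, that the table is mislabelled, or that efficacy is overstated. The primary endpoint counts each woman once and is unaffected. Nothing here bears on whether asymptomatic BV should be treated.

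**What to change.** - In SAP 8.3, for the exploratory outcome only, define a new episode as a positive visit preceded by at least one BV-negative evaluable visit since the last positive, whether or not MetroGel was given in between. Consecutive positives are one episode.
- Add to Table 67, by arm, the number of episodes and the number and proportion of women with two or more by Visit 4, as description. Keep the current count as a row labelled 'visits with BV'.
- If episodes are modelled as a rate, take time spent in an ongoing episode out of the offset.
- As a sensitivity analysis, count a positive after a completed MetroGel course as a new episode. This also supplies the re-treatment analysis that Protocol 11.6.4.3 promised for these outcomes.

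The cost is SAP wording and one derived variable from data already collected (visit diagnoses and concomitant medications). The drawbacks are fewer counted events, a wider interval, and a rule that cannot see clearance and re-acquisition between two positive visits. Re-treatment can still influence whether a negative visit occurs, but it no longer enters the scoring rule. Conduct, sample size, primary endpoint and clinical management stay as they are.
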